4.6 Rationale for Public Health Emergency mitigation procedures

During a Public Health emergency as declared by Local or Regional authorities i.e. pandemic, epidemic or natural disaster, mitigation procedures to ensure subject safety and trial integrity are listed in relevant sections. Notification of the Public health emergency should be discussed with Novartis prior to implementation of mitigation procedures and permitted/approved by Local or Regional Health Authorities and Ethics Committees as appropriate.

5 Population

The subject population will include male and female subjects aged ≥ 28 days to < 18 years, who have undergone alloSCT with a successful donor-derived myeloid engraftment and have been diagnosed with either treatment-naïve moderate to severe cGvHD or steroid-refractory moderate to severe cGvHD as defined by NIH 2014 Consensus Criteria ([Jagasia et al 2015](#), [Martin et al 2015](#)). It is important that the NIH criteria are strictly applied and it is recommended that the diagnosis of cGvHD requires at least one pathognomonic manifestation of cGvHD or, if a pathognomonic feature is not present, at least one distinctive manifestation of cGvHD supported by histologic evidence of GvHD from any site ([Socié and Ritz 2014](#), [Jagasia et al 2015](#)). These data must be documented in the source documentation and results should be made available upon request.

The investigator or designee must ensure that only subjects who meet all the following inclusion and none of the exclusion criteria are offered treatment in the study.

5.1 Inclusion criteria

Subjects eligible for inclusion in this study must meet **all** of the following criteria:

1. Male or female subjects age ≥ 28 days and < 18 years at the time of informed consent.
2. Subjects who have undergone a successful alloSCT from any donor source (matched unrelated donor, sibling, haplo-identical) using bone marrow, peripheral blood stem cells, or cord blood. Recipients of myeloablative or reduced intensity conditioning are eligible.
3. Subjects with diagnosed moderate to severe cGvHD according to NIH 2014 Consensus Criteria ([Section 16.2](#)) prior to Cycle 1 Day 1. Other possible diagnoses for clinical symptoms supporting the cGvHD diagnosis must be excluded (e.g. infection, drug side effects, malignancy). Subjects must be either:
 - Treatment-naïve cGvHD subjects that have not received any prior systemic treatment for cGvHD except for a maximum 72h of prior systemic corticosteroid therapy of methylprednisolone or equivalent after the onset of chronic GvHD. Subjects are allowed to have received prior systemic treatment for cGvHD prophylaxis (as long as the prophylaxis was started prior to the diagnosis of cGvHD).

OR

- Steroid-refractory moderate to severe cGvHD as per institutional criteria, or per physician decision in case institutional criteria are not available, and still receiving systemic corticosteroids for the treatment of cGvHD for a duration of < 18 months prior to Cycle 1 Day 1; in case the corticosteroids were previously interrupted due to response, the duration of < 18 months applies to the last period of corticosteroids use.

4. Able to swallow study medication or administer the ruxolitinib pediatric formulation by nasogastric (NG) tube, as applicable.
5. Written study informed consent (and assent if appropriate) from the subject and/or parent/legal guardian

5.2 Exclusion criteria

Subjects meeting any of the following criteria are not eligible for inclusion in this study.

1. SR-cGvHD subjects with a prior cGvHD treatment with a JAK1- or a JAK2- or a JAK1/2-inhibitor are not allowed, except when the subject achieved complete or partial response and has been off JAK inhibitor treatment for at least 4 weeks prior to Cycle 1 Day 1, or up to 5 times the half-life of the prior JAK inhibitor, whichever is longer.
2. Subjects who initiated systemic calcineurin inhibitors (CNI; cyclosporine or tacrolimus) within 3 weeks prior to the start of ruxolitinib on Cycle 1 Day 1. Note: Systemic CNI are allowed when initiated > 3 weeks from start of ruxolitinib.
3. Failed prior alloSCT within the past 6 months; subjects with relapsed primary malignancy, or who have been treated for relapse after the alloSCT was performed, or who require withdrawal of immune suppression as pre-emergent treatment of early malignancy relapse.
4. Significant respiratory disease including subjects who are on mechanical ventilation or who have a resting oxygen saturation < 90% by pulse-oximetry on room-air.
5. Impairment of gastrointestinal (GI) function (unrelated to GvHD) or GI disease (unrelated to GvHD) that may significantly alter the absorption of oral ruxolitinib (e.g., ulcerative diseases, uncontrolled nausea, vomiting, diarrhea, malabsorption syndrome or small bowel resection).
6. Cholestatic disorders, or unresolved sinusoidal obstructive syndrome/veno-occlusive disease of the liver (defined as persistent bilirubin abnormalities not attributable to cGvHD and ongoing organ dysfunction).
7. Presence of clinically active uncontrolled infection including significant bacterial, fungal, viral or parasitic infection requiring treatment. Infections are considered controlled if appropriate therapy has been instituted and, at the time of screening, no signs of progression are present. Progression of infection is defined as hemodynamic instability attributable to sepsis, new symptoms, worsening physical signs or radiographic findings attributable to infection. Persisting fever without other signs or symptoms will not be interpreted as progressing infection.
8. Known human immunodeficiency virus (HIV) infection.
9. Evidence of uncontrolled hepatitis B virus (HBV) or hepatitis C virus (HCV) based on assessment done by Investigator or delegate.
10. cGvHD occurring after a non-scheduled donor lymphocyte infusion (DLI) administered for pre-emptive treatment of malignancy recurrence. Subjects who have received a scheduled DLI as part of their transplant procedure and not for management of malignancy relapse are eligible.
11. Any condition that would, in the investigator's judgment, interfere with full participation in the study, including administration of study drug and attending required study visits; pose a significant risk to the subject; or interfere with interpretation of study data.
12. Known allergies, hypersensitivity, or intolerance to any of the study medications, excipients, or similar compounds.
13. History of bone disorders such as osteogenesis imperfecta, rickets, renal osteodystrophy, osteomyelitis, osteopenia, fibrous dysplasia, osteomalacia etc. prior to the underlying diagnosis which resulted in the alloSCT.
14. History of endocrine or kidney related growth retardation prior to the underlying diagnosis which resulted in the alloSCT.
15. Female adolescent subjects who are pregnant or breast feeding.

16. Female subjects of childbearing potential (e.g., are menstruating) who do not agree to abstinence, or, if sexually active, do not agree to use highly effective contraception as defined in [Section 8.4.2](#). If local regulations are more vigorous than that from the contraception methods listed in [Section 8.4.2](#). to prevent pregnancy, local regulations apply and will be described in the ICF.
17. Evidence of clinically active tuberculosis (clinical diagnosis per local practice)
18. Any corticosteroid therapy for indications other than cGvHD at doses > 1 mg/kg/daymethylprednisolone (or equivalent prednisone dose 1.25 mg/kg/day) within 7 days of the screening visit.
19. Current therapy with systemic medications that interfere with coagulation or platelet function including but not limited to aspirin and related drugs, heparin, and warfarin (to minimize risk of bleeding). Note: Heparin or Low Molecular Weight Heparin (LMWH) is allowed if used at sub-therapeutic dose for e.g., prophylaxis of sinusoidal obstructive syndrome/veno-occlusive disease of the liver.
20. Subject is receiving fluconazole at daily doses higher than 6 mg/kg (maximum 200mg).
21. Subject is receiving and does not agree to stop herbal preparations/medications. These herbal medications include, but are not limited to, St. John's Wort, Kava, ephedra (ma huang), gingko biloba, dehydroepiandrosterone (DHEA), yohimbe, saw palmetto, and ginseng. Subjects must stop using herbal medications at least 7 days prior to first dose of study treatment. Refer to [Section 6.2.2](#)
22. History of progressive multifocal leuko-encephalopathy (PML).
23. Investigational treatment within 30 days prior to ruxolitinib treatment initiation or within 5 half-lives of the investigational product, whichever is greater.
24. Presence of severely impaired renal function (confirmed within 72h prior to ruxolitinib start) defined by:
 - Glomerular Filtration Rate (GFR) < 30 mL/min/1.73 m², using estimated creatinine clearance calculated by updated bedside Schwartz equation or Cockroft Gault equation,
 - or
 - renal dialysis requirement
25. Serious comorbid diseases as per investigator judgement
26. Life expectancy of less than 1 month as per investigator judgement.
27. Clinically significant or uncontrolled cardiac disease, including any of the following:
 - Acute myocardial infarction within 6 months from Cycle 1 Day 1 ruxolitinib administration
 - Uncontrolled hypertension
 - New York Heart Association Class III or IV congestive heart failure
 - Unstable angina within last 6 months from screening
 - Clinically significant (symptomatic) cardiac arrhythmias (e.g., sustained ventricular tachycardia, and clinically significant second or third degree AV block without a pacemaker, circulatory collapse requiring vasopressor or inotropic support, or arrhythmia requiring therapy).

6 Treatment

6.1 Study treatment

Study treatment includes:

- **Investigational treatment:**
 - Refers to ruxolitinib (investigational drug)
- **Other study treatment:**
 - Refers to the concomitant use of corticosteroids to treat treatment-naive cGvHD or SR-cGvHD

Ruxolitinib will be administered as a 5 mg ruxolitinib tablet or as ruxolitinib oral pediatric formulation twice a day.

- **Treatment-naive cGvHD:** In addition to ruxolitinib, treatment must include methylprednisolone (or equivalent prednisone)
- **SR-cGvHD:** In addition to ruxolitinib, concomitant use of corticosteroids is required

In addition to study treatment, subjects may receive standard alloSCT supportive care including anti-infective medications and transfusion support. Systemic immunosuppressive medications used for the prophylaxis of cGvHD may be continued after Cycle 1 Day 1 if initiated prior to diagnosis of cGvHD, i.e., not used as therapy but as continuation of prophylaxis. Dose adjustments of immunosuppressive prophylactic drugs with therapeutic intent or addition of systemic immunosuppressive medications for treatment of cGvHD are not allowed. Systemic CNIs may be continued after Cycle 1 Day 1 if initiated at least 3 weeks prior to the start of ruxolitinib, i.e. at Cycle 1 Day 1. CNI should be used at standard dosing and adjusted to therapeutic trough levels. Continued use of topical corticosteroid therapy for cGvHD per institutional guidelines are permitted. For SR-cGvHD subjects, cessation of other systemic treatment for cGvHD other than corticosteroids +/- CNI will be required prior to ruxolitinib initiation. Permitted concomitant medications are described in [Section 6.2.1.1](#).

6.1.1 Investigational and control drugs

Table 6-1 Dose and treatment schedule

Investigational treatment	Age groups	Pharmaceutical form and Route of Administration	Dose	Frequency and/or Regimen
Ruxolitinib (INC424)	Group 1 ≥ 12 years old to < 18 years old	5 mg tablet* for oral use OR oral pediatric formulation	10 mg BID (2 tablets orally BID) OR 10 mg BID oral pediatric formulation**	Twice per day
Ruxolitinib (INC424)	Group 2 ≥ 6 years old to < 12 years old	5 mg tablet* for oral use OR oral pediatric formulation*	5 mg BID (1 tablet orally BID) OR 5 mg BID oral pediatric formulation**	Twice per day

Investigational treatment	Age groups	Pharmaceutical form and Route of Administration	Dose	Frequency and/or Regimen
Ruxolitinib (INC424)	Group 3 ≥ 2 years old to < 6 years old	5 mg tablet* for oral use OR oral pediatric formulation	4 mg/m ² BID (either tablet orally OR oral pediatric formulation)**	Twice per day
Ruxolitinib (INC424)	Group 4 ≥ 28 days to < 2 years old	oral pediatric formulation	X mg/m ² BID (oral pediatric formulation)** To be defined from study CINC424F12201	Twice per day

*A whole tablet for oral use may be crushed as per instructions in the pharmacy manual (if calculated dose based on BSA is not 5 mg or 10 mg, then crushing is not permitted. Tablet cannot be broken to achieve partial doses. In this case, oral pediatric formulation should be administered). Oral pediatric formulation should be dispensed according to instructions in the pharmacy manual.
Note: Crushed tablet(s) can only be administered orally and cannot be administered by nasogastric (NG) tube.
**Calculated doses should be rounded to the nearest available volume as per instructions in the pharmacy manual

The Investigator will instruct the subject to take the investigational treatment as per protocol.

All dosages prescribed and dispensed to the subject and all dose changes during the study must be recorded on the Dosage Administration Record electronic case report form (CRF).

Ruxolitinib will be administered orally twice per day at the assigned dose based on age group, given as 5 mg tablets or equivalent dose as oral pediatric formulation.

Ruxolitinib (tablet or oral pediatric formulation) should be taken approximately 12 hours apart (morning and night) without regards to food. Ruxolitinib will be administered by Investigator or delegate, or self-administered by the subject or parent/legal guardian in an outpatient setting.

Subjects should be instructed not to take ruxolitinib at home on the days of the scheduled pre-dose blood collection for PK and biomarker samples. Refer to [Section 8.5.1](#) and [Section 8.5.2](#). Dosing will be administered after pre-dose blood collection at these visits.

If a dose is vomited within any timeframe after dosing, re-dosing should not occur.

If a dose is missed, the subject should not take an additional dose, but should take the prescribed dose at the next scheduled dosing time.

The ruxolitinib dose as assigned on Cycle 1 Day 1 (based on age) must **not** be changed until the subject completes the Cycle 7 Day 1 visit assessments, unless dose adjustments are needed to manage safety events. After Cycle 7 Day 1, the Investigator must re-evaluate the assigned ruxolitinib dose based on the subject's age and/or growth. Dosing based on growth should be adjusted if the newly calculated dose is a > 10% change from the previously calculated dose. Subjects should remain on the same formulation until Cycle 7 Day 1. Any change in formulation prior to Cycle 7 Day 1 requires approval from the Sponsor. All dose changes must be recorded on the Dosage Administration Record electronic case report form (eCRF).

6.1.2 Additional study treatments

The following non-investigational treatment will be taken during the treatment period by the subject as per standard of care:

- Systemic corticosteroids

Dose adjustments of immunosuppressive prophylactic drugs with therapeutic intent or addition of systemic immunosuppressive medications for treatment of cGvHD are not allowed.

6.1.3 Treatment arms/group

This is an open-label, single treatment arm study. There will be up to 4 age groups included in the study: Group 1 (Age \geq 12 years to $<$ 18 years), Group 2 (Age \geq 6 years to $<$ 12 years), Group 3 (Age \geq 2 years to $<$ 6 years) and Group 4 (Age \geq 28 days to $<$ 2 years).

6.1.4 Guidelines for continuation of treatment

Subjects may continue investigational treatment until one of the discontinuation criteria is met. Refer to [Section 6.5](#) for dose modifications and guidelines for continuation of treatment.

6.1.5 Treatment duration

The planned duration of study treatment is approximately 36 months (39 cycles).

The Treatment Period for each subject will begin on Cycle 1, Day 1 and continue until the end of Cycle 39 (Week 156), unless treatment change for any reason including treatment failure, e.g. cGvHD progression, mixed response or no response, or a GvHD flare as defined in [Section 6.1.5.2.1](#), intolerable toxicity, death, or withdrawal from the study for other reasons occurs.

During the Treatment period, the subjects' treatment will be managed according to their response as follows:

Subjects that achieve CR or PR: On Cycle 7 Day 1, subjects still receiving benefit from ruxolitinib may continue on ruxolitinib until the end of Cycle 39 (Week 156) and will follow the Visit Evaluation Schedule per [Table 8-1](#):

Subjects that achieve a CR or PR may taper corticosteroids at any time from two weeks of documented CR or PR. See [Section 6.1.5.2](#) for details

In subjects that achieve a CR or PR: A taper of ruxolitinib is allowed only on or after Cycle 7 Day 1.

- A taper of CNI is allowed after Cycle 7 Day 1.

Subjects who taper off ruxolitinib and all immunosuppressive therapy due to achieving a CR or PR will continue to follow the currently assigned Visit Evaluation Schedule ([Table 8-1](#)), including all safety and efficacy assessments, and will be monitored for cGvHD recurrence which must be reported in the database. Subjects experiencing cGvHD recurrence after tapering off ruxolitinib will be treated per Investigator discretion, which may include re-initiation of ruxolitinib and will follow the assigned Visit Evaluation Schedule ([Table 8-1](#)).

Subjects without CR or PR: If the subject is not receiving benefit from ruxolitinib therapy per investigator decision, the subject should discontinue ruxolitinib and be treated per institutional practice.

These subjects will enter the early discontinuation follow-up until completion of 39 cycles from their first dose of ruxolitinib.

Subjects who permanently discontinue ruxolitinib for reasons other than achieving a CR or PR prior to completion of 39 cycles on study will complete the safety follow-up visit and then follow the early discontinuation follow-up visit schedule (as described in [Table 8-1](#)). These subjects may be treated per Institutional practice.

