6.1.5.2 Tapering Guidelines

Tapering of corticosteroids, CNI, and ruxolitinib will follow 2 steps: first taper systemic corticosteroids following documented CR or PR, and follow with taper of CNI/ruxolitinib.

The taper of corticosteroids, in responding subjects (CR or PR) as outlined in [Table 6-2](#), must not be attempted earlier than approximately 2 weeks from the time of documented CR or PR. In responding subjects, the taper of ruxolitinib must not be attempted until the subject is off corticosteroids and CNIs AND the subject has completed the assessments for Cycle 7 Day 1.

During the Treatment Period, immunosuppression taper guidelines are:

- **Corticosteroids:** Every effort should be made to use the minimum dose of corticosteroid that is sufficient to control cGvHD manifestation. It is recommended that a taper of corticosteroids should be attempted approximately two weeks after achieving a documented CR or PR. Guidelines are included in [Table 6-2](#). If a flare should occur during the taper, the treatment should continue for at least 3 months prior to attempting to resume the taper.

Table 6-2 Corticosteroid taper guidelines

Week (time from achieving a CR or PR)	Dose, mg/kg body weight
0	Current dose of corticosteroid every (Q) day (example 1 mg)
2	Current dose of corticosteroid (1 mg)/ decrease alternate day dose by 50%* (0.5 mg)
4	Current dose of corticosteroid (1 mg)/decrease alternate day dose by 50%* (0.25 mg)
6	Current dose of corticosteroid every other day (QOD): 1 mg every other day
8	Decrease current dose of corticosteroid by 10% every 2 weeks until off

*Alternate-day administration
([Flowers and Martin, 2015](#))

- **CNI (cyclosporine or tacrolimus):** Once off systemic corticosteroids, and documented CR or PR, starting at Cycle 7 Day 1 at 25% dose reduction per month is allowed, or to be tapered per institutional practice.

- **Ruxolitinib:** Once off systemic corticosteroids, ruxolitinib taper is allowed in subjects demonstrating a CR or PR, starting no earlier than Cycle 7 Day 1. The following guidance may be followed based on evaluation of patient condition, current dosing regimen and the clinical judgement of Investigator: a 50% dose reduction every 2 months (approximately 56 days) can be initiated. If sustained cGvHD response is observed (i.e. no worsening of cGvHD signs and symptoms), subject can be further tapered by a second 50% dosage reduction based on investigator assessment and judgement.

6.1.5.2.1 cGvHD Flare

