6.5.1 Dose modifications

For subjects who do not tolerate the protocol-specified dosing schedule, dose interruptions and/or reductions are either recommended or mandated in order to allow subjects to continue ruxolitinib.

These dose modifications are summarized in [Table 6-3](#). Deviations to mandatory dose interruptions and/or reductions are not allowed. Permanent treatment discontinuation is mandatory for specific events indicated as such in [Table 6-3](#).

Based on the subject's age, the ruxolitinib dose will not exceed the starting dose level defined for that age Group. The dose for CNI and/or corticosteroids can be modified as per Investigator discretion, institutional guidelines, or as per product label.

A standardized dosing paradigm in [Table 6-4](#) and [Table 6-5](#) will be used to determine dose adjustments for safety and efficacy so that each subject is titrated to their most appropriate dose. These dose changes must be recorded on the Dosage Administration Record eCRF.

A more frequent schedule of safety assessments is recommended (i.e. every 2 weeks) after restarting ruxolitinib due to a dose hold.

If a subject requires a dose interruption of > 21 days from ruxolitinib, then the subject must be permanently discontinued from ruxolitinib, and will be entered into early discontinuation follow-up with assessments as described in [Table 8-1](#).

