9.1 Discontinuation

9.1.1 Discontinuation of study treatment

Discontinuation of investigational treatment for a subject occurs when treatment is stopped earlier than the protocol planned duration, and can be initiated by either the subject or the investigator.

The investigator must discontinue investigational treatment for a given subject if, he/she believes that continuation would negatively impact the subject's well-being.

In addition to mandatory investigational treatment discontinuation listed in [Table 6-3](#), investigational treatment must also be discontinued under any of the following circumstances:

- Lack of efficacy of chronic GvHD treatment ([Section 16.4](#)).
- Lack of clinical benefit according to the Investigator.
- Underlying disease recurrence, or relapse ([Section 8.3.1.3](#)).
- Evidence of graft failure necessitating rapid taper of immunosuppression, administration of non-scheduled DLI, stem cell boost and/or chemotherapy, or other treatment that would expectedly affect chronic GvHD ([Section 8.3.2](#)).

- The following deviations from the prescribed dose regimen for investigational treatment:
- Dose hold > 21 days for ruxolitinib ([Section 6.5.1](#)).
- Adverse events leading to investigational treatment discontinuation. ([Section 6.5.1](#)).
- Pregnancy ([Section 8.4.2](#))
- Protocol deviation that results in a significant risk to the subject's safety including use of prohibited treatment ([Section 6.2.2](#)).

Subjects who discontinue ruxolitinib should NOT be considered withdrawn from the study. The subject should return for the early discontinuation follow-up assessments as indicated in [Table 8-1](#). Assessments will include:

- Height and weight
- Tanner staging (if appropriate)
- Graft failure assessment
- Hematologic underlying disease relapse/progression assessment
- Infection monitoring
- Second primary malignancy assessment
- Survival follow-up

The follow-up for subjects that permanently discontinue ruxolitinib early includes visits every 6 months until the subject reaches 3 years (39 cycles) from the date of their first ruxolitinib dose (see [Table 8-1](#)). In case the time between treatment discontinuation and 3 years (39 cycles) from the date of the first ruxolitinib dose is less than 6 months, subjects will be required to return for the one final early discontinuation follow-up visit as per [Table 8-1](#).

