2.4 Treatments (study treatment, rescue medication, concomitant therapies, compliance)

2.4.1 Study treatment / compliance

Duration of exposure to ruxolitinib will be summarized by Age group and by means of descriptive statistics. It will also be categorized into time intervals; frequency counts and percentages will be presented for the number (%) of patients in each interval.

Total daily dose, actual cumulative dose, dose intensity (DI) and relative dose intensity (RDI) will be summarized for ruxolitinib by Age group.

The number (%) of patients who have dose reductions or interruptions, and the reasons, will be summarized for ruxolitinib by Age group.

Patient level listings of all doses administered on treatment along with dose change reasons will be produced by Age group.

The Safety Set will be used for all summaries and listings of study treatment.

If more than one dose and/or formulation is assigned within one Age group, then summaries and listings will be reported by Age group as well as doses/formulation within the Age group

Duration of follow-up

The duration of follow-up time is defined as (date of last contact) – (date of first administration of investigational treatment) + 1.

Duration of exposure to investigational treatment

Duration of exposure to investigational treatment (days) = (last date of exposure to investigational treatment) – (date of first administration of investigational treatment) + 1.

If any subjects tapered off ruxolitinib and re-started ruxolitinib treatment due to cGvHD recurrence, two different definitions of duration of exposure will be distinguished:

- **Duration of exposure including taper off periods** is defined as the time from first to very last date of ruxolitinib treatment, which includes the intervening period without treatment.
- **Duration of exposure excluding taper off periods** is defined as above but deduct the intervening period without treatment for subjects who taper off and restart after cGvHD recurrence. These periods are captured as dose interruption with reason “dose tapering following response”.

Summary of duration of exposure of investigational treatment in days will include categorical summaries (based on clinically meaningful time intervals) and continuous summaries (i.e. mean, standard deviation etc.) using appropriate units of time.

Duration of exposure to investigational treatment in patient-years

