2.5.4 Supportive analyses

Supportive analysis will include:

- A detailed description of response rates (CR, PR, Unchanged, mixed response and progression) at Cycle 7 Day 1
- A detailed description of the organ-specific response for all organs at Cycle 7 Day 1
- If at least 18 subjects are enrolled with either first line vs. SR-cGvHD respectively, the ORR will be explored for treatment naive and SR subgroup subjects.
This and further subgroups are described in [Section 2.2.1](#).

The supportive analyses will be performed on the FAS.

In addition, a sensitivity analysis will be done, where subjects with protocol deviations that may affect the primary endpoint are excluded from the analysis. These are following:

- Prohibited concomitant medication administered during treatment period (COMD01)
- Treatment naive or steroid refractory cGvHD corticosteroid treatment criteria not met (INCL04B)
- Missing individual organ assessment at C1D1 (unless not possible) (OTH02)
- Missing individual organ assessment at C4D1 or C7D1 (unless not possible) (OTH03)
- Starting dose of study drug (ruxolitinib) not per protocol-defined age-based schedule (Group 1 and 2) (TRT01)
- Starting dose of study drug (ruxolitinib) not per protocol-defined age-based schedule (Group 3 and 4) (TRT02)
- In treatment naive cGvHD subjects, in addition to ruxolitinib, methylprednisolone (or equivalent prednisone) treatment was initially not given as part of study treatment (TRT03)
- Patient did not take the ruxolitinib assigned dose (TRT08)
- The ruxolitinib dose assigned on C1D1 (based on age) was changed before the subject completed C7D1 assessments (excluding dose adjustments for safety) (TRT09)

- Corticosteroid taper was initiated earlier than allowed as per protocol (excluding dose adjustments for safety) (TRT13)
- Subject had a dose interruption of >21 days from ruxolitinib but was not permanently discontinued from ruxolitinib (WITH01)
- Individual organ response assessment / overall response assessment not as per protocol response criteria (OTH14)
- Patient was not compliant with study drug (Ruxolitinib); More than 7 days of consecutive insufficient treatment or overdosing or cumulated insufficient treatment over a period of 24 weeks is observed (TRT16)

Supportive analysis will be purely exploratory and are intended to explore the consistency of treatment effect. No inferential statistics (p-values) will be produced for the subgroups.

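### The WITH01 exclusion in SAP 2.5.4 has no time limit, so ruxolitinib interruptions after Cycle 7 Day 1 can remove children from the sensitivity analysis of Cycle 7 Day 1 response

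*Protocol*

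**What the plan says.** SAP 2.5.4 plans a sensitivity analysis of ORR at Cycle 7 Day 1 (C7D1) that leaves out subjects with deviations thought able to influence that endpoint. The listed codes include "Subject had a dose interruption of >21 days from ruxolitinib but was not permanently discontinued from ruxolitinib (WITH01"). The wording limits neither the date of the interruption nor its reason.

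Protocol 6.1.5 lets a child in CR or PR taper off: "A taper of ruxolitinib is allowed only on or after Cycle 7 Day 1". Section 6.1.5.2 adds that the child must be off corticosteroids and CNIs and have completed the C7D1 assessments. For a later recurrence, 6.1.5 says "Subjects experiencing cGvHD recurrence after tapering off ruxolitinib will be treated per Investigator discretion, which may include re-initiation of ruxolitinib", with no limit on the time off drug.

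SAP 2.1.1 and 2.4.1 say how that time is recorded when a child restarts: "These periods are captured as dose interruption with reason" dose tapering following response.

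Elsewhere, protocol 6.5.1 says "If a subject requires a dose interruption of > 21 days from ruxolitinib, then the subject must be permanently discontinued from ruxolitinib". Section 9.1.1 lists "Dose hold > 21 days for ruxolitinib" among the mandatory stops, and 9.2 bars further in-study ruxolitinib for anyone who meets a 9.1.1 criterion. None of the three mentions taper-off for response.

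**The concern.** A sensitivity analysis of this kind should remove events that could have changed the result. A ruxolitinib gap that opens after the C7D1 assessment could not have done so, yet WITH01 as worded removes the child anyway. The clearest example is a responder who tapers off after C7D1, is drug-free for more than 21 days and restarts as 6.1.5 allows. The SAP stores that gap as an interruption, so the child fits the WITH01 wording without having departed from 6.1.5.

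At stake is how the sensitivity result reads. If it differs from the primary ORR for this reason, the difference says nothing about robustness. There is also a question for sites, because the restart permission and the 21-day text are not cross-referenced.

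**Working it through.** **1. The plan's own figures.** Inputs: exact two-sided 90% interval (protocol 12.4.2, SAP 2.5.2), assumed true ORR 70% and planned n = 42 (protocol 12.8.1), 46 enrolled (protocol, Amendment 2 summary). The Clopper-Pearson lower limit is the 5% quantile of Beta(r, n − r + 1). For n = 42 the smallest r with a lower limit of at least 50% is 27, with interval 0.505 to 0.765 and P(X ≥ 27 | 42, 0.70) = 0.836. This matches Table 12-1, and all 21 rows of that table (n = 30 to 50) reproduce. At n = 46 the minimum is 30, with lower limit 0.521.

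**2. Timing.** C7D1 is study day 6 × 28 + 1 = 169. The taper guidance reads "a 50% dose reduction every 2 months (approximately 56 days) can be initiated", with a possible second step.
- Off drug after one step: 169 + 56 = day 225. A gap of more than 21 days is reached at 225 + 22 = day 247.
- Off drug after two steps: 169 + 112 = day 281. The gap is reached at 281 + 22 = day 303.

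These are early dates, since corticosteroids and CNIs must be stopped first. Under this guidance the gap follows the C7D1 assessment. It can still fall before the interim cut-off, which waits until every subject has had one year of treatment or has stopped.

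**3. Effect of each removal.** Taking out one responder changes ORR by r/n − (r − 1)/(n − 1) = (n − r)/[n(n − 1)].
- 27/42: 15/(42 × 41) = 0.9 points down
- 30/46: 16/(46 × 45) = 0.8 points down
- 32/46: 14/(46 × 45) = 0.7 points down

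Taking out one non-responder raises ORR by r/[n(n − 1)]; for 27/42 that is 27/(42 × 41) = 1.6 points.

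**4. Scenarios.** The number removed is an assumption, because the documents do not give it.

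| Start | Removed | Result | ORR | 90% lower limit |
|---|---|---|---|---|
| 27/42 | none | 27/42 | 64.3% | 50.5% |
| 27/42 | 1 responder | 26/41 | 63.4% | 49.4% |
| 27/42 | 5 responders | 22/37 | 59.5% | 44.6% |
| 27/42 | 1 responder, 1 non-responder | 26/40 | 65.0% | 50.8% |
| 27/42 | 2 non-responders | 27/40 | 67.5% | 53.4% |
| 30/46 | none | 30/46 | 65.2% | 52.1% |
| 30/46 | 1 responder | 29/45 | 64.4% | 51.1% |
| 30/46 | 3 responders | 27/43 | 62.8% | 49.1% |
| 30/46 | 5 responders | 25/41 | 61.0% | 46.9% |
| 32/46 | none | 32/46 | 69.6% | 56.6% |
| 32/46 | 5 responders | 27/41 | 65.9% | 51.9% |

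Averaged over five responders, the fall per child is (64.3 − 59.5)/5 = 1.0 point from 27/42 and (65.2 − 61.0)/5 = 0.8 from 30/46.

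**5. Wording of neighbouring codes.** In the same list, TRT09 counts only dose changes before the C7D1 assessments were completed and leaves out safety adjustments. OTH03 names its visits. WITH01 has neither kind of limit.

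**The case against.** A reader might infer that WITH01 removes only responders and so biases the sensitivity ORR downward. The wording does not support that. It covers any interruption over 21 days in any subject who was not permanently discontinued, so a non-responder with a long toxicity hold is caught too, and removing that child raises ORR. Even on the taper route, 6.1.5 asks for CR or PR at the time of taper, so a late responder who was a C7D1 non-responder could be among those removed.

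A reader might also infer that a restarting child is necessarily coded WITH01. That is not settled. WITH01 is a protocol-deviation code, the SAP works from deviations entered in the database, and a restart that 6.1.5 permits need not be entered as one. The separate reason code would let the team tell these gaps apart. However, no such exemption is written.

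A third inference is that the protocol flatly contradicts itself. Section 6.5.1 opens "For subjects who do not tolerate the protocol-specified dosing schedule, dose interruptions and/or reductions are either recommended or mandated", 6.5.1.1 and 6.5.1.2 tie the 21 days to resolution of toxicity, and 9.1.1 lists the hold under departures from the prescribed regimen. Sections 6.1.5 and 6.5.1.2 send to early-discontinuation follow-up those who stop for reasons other than CR or PR. A toxicity-only reading is therefore available. What stands is that neither 6.5.1 nor 9.1.1 states it, and the SAP's use of the term dose interruption for the gap leaves the literal reading open.

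Finally, crossing 50% in some scenarios is not a failed criterion. Both 27/42 and 30/46 are the smallest passing counts in Table 12-1, the 50% figure is a planning target, and the plan tests no hypothesis.

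**Conclusion.** The concern holds as a minor defect in a stated rule: WITH01 in SAP 2.5.4 lacks a time limit, so interruptions that cannot bear on C7D1 response lead to exclusion. On the taper-and-restart route the effect would mostly be to remove C7D1 responders and lower the sensitivity ORR by about 0.8 to 1.0 points per child from 27/42 or 30/46, and by about 0.7 from 32/46. The direction for WITH01 as a whole is not fixed.

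This rests on assumed response counts, on the planned 42 or enrolled 46 as the denominator, and on such gaps being entered as deviations. The documents do not say how many children restarted, or whether any did so before the interim cut-off. SAP 2.5 does not repeat the analysis for the final CSR if the data are unchanged. The FAS primary analysis is unaffected, and the supportive analyses are described as exploratory. The protocol passages need reconciling because the exemption is unwritten, not because the two rules are shown to be incompatible.

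**What to change.** In SAP 2.5.4, apply WITH01 only to interruptions that occurred before the assessment used for C7D1, and say how an interruption that straddles that date is counted. This one sentence also takes out every response-taper gap, since a taper cannot start before C7D1, and it works whichever clinical rule the protocol adopts. It needs only the dates of the interruption and of the C7D1 assessment.

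Separately, reconcile protocol 6.1.5 with 6.5.1, 9.1.1 and 9.2 so that the text states whether the 21-day limit covers drug-free time after taper-off for response. Which rule applies is for the sponsor's clinical team. The cost is one clarifying sentence, cross-referenced where needed.
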